24. Urine tests: pH, concentration, protein, glucose, red blood, white blood cell count
25. CD4 lymphocyte count; HIV-viral load; AIDS status
26. HIV-therapy: drug name and dose (only ongoing treatment); previous switch to other regimens for virological failure
27. Questionnaires to address cognitive status: Cognitive Failure Questionnaire (CFQ), Mini-Mental State Examination, Clinical Dementia rating Scale, Montreal Cognitive Assessment (MOCA).
28. Results of SARS-CoV-2 molecular test on amniotic fluid
29. Weight, height/length, cranial circumference, BMI
30. Type of transplant (heart, lung, kidney, liver, pancreas); single-combined; year of transplantation
31. Graft function: good, impaired, failure, rejection acute-chronic, recurrence of underlying disease, other
32. Immunosuppressive regimen: drug name and dose
33. According to Common Terminology Criteria for Adverse Events (CTCAE)
34. At least one of three timepoints (month 3, month 6, month 12) is required to perform metagenomics analysis.
35. At least one of the three timepoints (month 3, month 6, month 12) is required.

Table 2. Schedule of post-vaccination assessments

| | 1 st dose | 2 nd dose ² | 3 months (± 1 month)* | 6 months (± 2 months)* | 12 months (± 3 months)* |
|--|----------------------|-----------------------------------|--------------------------|---------------------------|----------------------------|
| Baseline information¹ | | | | | |
| Underlying fragile condition | X ¹ | X ¹ | | | |
| Healthcare setting (i.e. LTCF) | X ¹ | X ¹ | | | |
| Comorbidities | X ¹ | X ¹ | | | |
| Concomitant medical treatments | X ¹ | X ¹ | | | |
| Past and/or new COVID-19 disease ³ | X ¹ | X ¹ | X | X | X |
| Clinical evaluation | | | | | |
| Relevant medical new events ⁴ | X | X | X | X | X |
| Clinical symptoms suggestive of COVID-19 | X | X | X | X | X |
| Lab assessment | | | | | |
| Whole blood count | X | X | | | |
| CD4/CD8 count | X | X | | | |
| IgG level | X | X | | | |
| C3 level | X | X | | | |
| Immunology | | | | | |
| Immune - serology and type I IFNs autoantibodies | X | X | X | X | X |
| Immune - cytokine and chemokine | X | X ⁷ | X ⁷ | X ⁷ | X ⁷ |
| Immune - cellular | X | X ⁷ | X ⁷ | X ⁷ | X ⁷ |
| Microbiological tests-NP swabs | | | | | |
| Viral variant and metagenomics sequencing | X ⁵ | X ⁵ | X ⁶ | X ⁶ | X ⁶ |
| EDTA whole blood | | | | | |
| Genetic and epigenetic analysis | X | | X | X | X |
| Stool Sample (faeces or rectal swab) | | | | | |

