6. STUDY RATIONALE

Since the beginning of COVID-19 pandemic, several special settings have been identified regarding the susceptibility to SARS-CoV-2 infection, the associated clinical spectrum and outcome. They include pregnant women, pediatric patients, elderly in particular those whole live in long-term care facilities (LTCFs), and immunocompromised hosts including solid organ transplant recipients (SOT), hematopoietic stem cell transplant (HSCT) recipients and patients with cancer.

Among pregnant women and children, asymptomatic or mild diseases have been frequently reported, prompting controversial concerns about their role in the infection transmission in community and hospital settings (1, 2). On the other hand, a high impact of COVID-19 on morbidity and mortality has been described in elderly and immunocompromised hosts (3, 4). Thus, optimization of prevention strategies, screening practices and therapeutic management is strongly advocated in fragile patients (5, 6). Indeed, these settings have been established as priority groups for vaccines. However, safety and efficacy of vaccination in these populations should be careful

assessed. Thus, preliminary epidemiological data are strongly needed to design further intervention trials and health policies.

Besides, an increasing body of evidence suggests that the gut microbiota plays a role in determining the severity of COVID-19, possibly through the modulation of immune responses (8, 9). Furthermore, dysbiosis of the gut microbiota could contribute to the persistence of symptoms, even after the resolution of the disease (10). For the same reasons, the microbiota could be involved in the onset of adverse reactions induced by vaccination, especially in fragile populations, as recently discussed (11). Defining the impact of the microbiota on immunity to vaccination and therefore on its effectiveness is currently considered a priority in various clinical settings (12).

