9.1. University of Bologna (UNIBO) – Italy

UNIBO will participate in the recruitment of the following COVID-19 and non-COVID-19 fragile populations: HIV positive, solid organ transplant recipients (liver, kidney, heart, lung),

hematopoietic stem cell transplant recipients, patients with cancer and autoimmune disease patients.

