11. STUDY PROCEDURES

In Figure 1, a study work flow is shown.

Figure 1: study work flow

All included patients will be evaluated during the scheduled visits for the underlying condition. During such visits, the following actions are required:

- Distribution of a questionnaire to capture the impact of COVID-19 pandemic on the socio-economic indicators, on the access to health care services, and to investigate risk perception and behavior towards preventing infection and COVID-19 disease, including vaccine acceptance. This questionnaire should be administered at two different time-points with an interval of at least 6 months to capture changes in behavior over the study period (Annex 1a or Annex 1b in case of children cohorts).

- Distribution of psychological scale questionnaires to investigate the impact of lockdown measures on mental health (Annex 2).
- Screening for past and/or current COVID-19 disease by medical interview, serology determination and nasopharyngeal swab or saliva specimens' collection.
- Collection, processing and storage of plasma for cytokine and chemokine analysis.
- Collection, processing and storage of serum for the subsequent sero-neutralization and type I IFNs autoantibodies detection.
- Collection, processing and storage of PBMCs for the subsequent anti-COVID-19 cellular immunity analysis.
- Collection, processing and storage of whole blood for genetic and epigenetic analysis.
- Collection, processing and storage of nasopharyngeal samples for SARS-CoV-2 detection and variant identification if clinically relevant.
- Collection, processing and storage of stool samples for metagenomic sequencing.
- In immunocompromised fragile cohorts, laboratory tests to assess the baseline “net state of immunosuppression” including whole blood count, lymphocyte differentiation, immunoglobulin levels, and complement (C3) levels should be done at the baseline (first clinical evaluation).

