During the post-vaccination monitoring and in the onset of a breakthrough infection after one or two doses of the anti-SARS-CoV-2 vaccine, several analyses (genomic, transcriptomic, cytokine, viral, genetic and epigenetic) will be performed in a local or centralised laboratory according to the type of testing realized (see Table 3):

- PBMCs for characterisation of T-cell immune response will be sent to University of Antwerpen
- Plasma for cytokinome analysis will be sent to University of Antwerpen
- Serum for autoantibodies against type I IFNs detection will be sent to INSERM or University of Antwerpen
- Whole blood samples for epigenetic and genetic analysis will be sent to UNIBO, INSERM and HMGU. In-depth human genetic analysis will be conducted using WGS or whole exome sequencing (WES) followed by functional analyses of the most promising variants.
- Nasal swabs for characterization of viral markers and respiratory microbiome dynamics will be sent to University of Antwerpen or INSERM.
- Stool samples for intestinal microbiome profiling will be sent to University of Bologna.

Detailed instructions on sample collection, processing, storage, shipment and destination sites are provided in the WP6 protocol (WP6, D 6.1) attached as Annex 4.

Table 3 – Overview of samples collection, processing, storage and destination sites.

| Sample | Aliquot | Sample type | Volume | Storage solution | Storage temp. (°C) | Shipping temp. (°C) | Task | Comment | Partner |
|-----------------------------|----------------|---|---|---|---|---------------------|--|--|--------------------|
| PBMC | 1 or 2 samples | PBMC | | 0.5 ml FBS/DMSO 20% | -70°C or below or liquid nitrogen | Dry ice | Characterisation of T-cell immune response | | UANTWERPEN |
| Blood | 1 | EDTA plasma, but heparin plasma or serum can also be used, if EDTA plasma is absolutely unavailable | 350 µL | EDTA plasma has to be processed according to the protocol provided before freezing (preferably at -80°C directly) | Short term at -20 °C, long term at -70°C or below | Dry ice | Cytokine analysis | Please process and freeze within 2 hours. | UANTWERPEN |
| | 2 | Serum/plasma | 200 µL | NA | -20°C, long term at -70°C or below | Dry ice | Auto-antibodies against type I IFNs | If available | INSERM |
| | 3 | Serum | 100 µL | NA | -20°C, long term at -70 ° or below | Dry ice | Antibodies detection | | INSERM; UANTWERPEN |

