| Whole blood | 1 | Extracted DNA or whole blood | 4 µg if DNA, 2 ml if whole blood | NA | -20°C/ -80°C | Dry ice | NGS of COVID-19 cohorts | DNA could be extracted locally or at HMGU. | INSERM/UNIBO |
| | 2 | DNA or whole blood | 750 ng in 45 µL if extracted DNA; otherwise 1 aliquot | TE buffer or water if extracted DNA | -20°C | Dry ice | Illumina EPIC DNA methylation | DNA could be extracted locally or at HMGU. | HMGU |
| NP swab | 1 | NP swab | 400 µL | TRIzol; RNA later; DNA/RNA shield | -70°C or below | Dry ice | Characterisation of viral markers Respiratory microbiome dynamics | | UANTWERPEN- INSERM |
| Stool sample or rectal swab | 1 | Stool (faecal swab if stool is unavailable) | 1-2 g | RNA later if possible, otherwise frozen. | +4°C (up to 24 h) long term at -70°C or below | Dry ice | Intestinal microbiome profiling | | UNIBO |

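### Blood is the only source of host DNA and graft type is not recorded, so a sequenced recipient of an allogeneic stem cell graft would contribute the donor's genotype as if it were the patient's own

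*Protocol*

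**What the plan says.** **Who is enrolled.** Section 6 names "hematopoietic stem cell transplant (HSCT) recipients" among the immunocompromised groups of interest. Section 9.1 lists, for the Bologna centre, "hematopoietic stem cell transplant recipients, patients with cancer and autoimmune disease patients". Section 10 excludes only people who do not consent.

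**What is collected.** Section 11 opens with "All included patients will be evaluated during the scheduled visits for the underlying condition". One of the actions it then requires at those visits is "Collection, processing and storage of whole blood for genetic and epigenetic analysis".

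**What is done with it.** Section 11 states "Whole blood samples for epigenetic and genetic analysis will be sent to UNIBO, INSERM and HMGU" and continues "In-depth human genetic analysis will be conducted using WGS or whole exome sequencing (WES) followed by functional analyses of the most promising variants". In Table 3, the whole-blood row for sequencing gives the sample type as "Extracted DNA or whole blood", and a second whole-blood row serves the EPIC methylation array. Annex 4 (the WP6 sampling document, Table 1) also assigns human sequencing and epigenomics to EDTA whole blood.

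**What the result is for.** Section 7 sets the aim of finding genetic markers and epigenetic features in the frail patients themselves. Annex 4, Section 2.6, says the methylation work will separate inherited from acquired regulatory features.

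**What is recorded about transplants.** The Table 1 footnote on transplant information (numbered 30 in the footnote list; the row carries marker 31) reads "Type of transplant (heart, lung, kidney, liver, pancreas); single-combined; year of transplantation". The medical-history footnote of Table 1 names solid organ transplantation only. Annex 3, the vaccine adverse-event form, has a stem cell transplant tick box and asks for further detail only for solid organs.

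**The concern.** An allogeneic stem cell graft replaces the recipient's blood-forming cells with the donor's. DNA extracted from blood afterwards is wholly or largely donor DNA. This is general biology and rests on no cited source. If such a patient is sequenced as the protocol describes, that patient's infection, severity or vaccine response is paired with another person's inherited genome.

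Two uses are exposed. The first is the search for variants to carry into functional work, where one or a few carriers can be decisive. The second is the contrast of inherited with acquired features in Annex 4, which presupposes that the inherited part belongs to the patient.

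The specimen and the data fields are set in the protocol itself. A later analysis plan can choose how to treat a stratum, but it cannot define that stratum by graft type if graft type was never collected.

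**Working it through.** The protocol gives no sample size for the genetic work, no count of stem cell recipients and no graft-type split, so there is no stated figure to reproduce. The check is mainly a reading of the text, with a short calculation to judge size.

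**Step 1: is another host-DNA source available?**
- The nasopharyngeal swab serves viral sequencing and the respiratory microbiome.
- Stool or rectal swab serves the gut microbiome.
- Serum, plasma and PBMC serve serology, autoantibodies, cytokines and cellular immunity.
- Whole blood serves sequencing and methylation.

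The extracted-DNA option in Table 3 stands in the whole-blood rows, with a comment that extraction may be done locally or centrally. It is therefore DNA from the same blood. Neither the protocol nor Annex 4 mentions tissue outside the blood system, pre-transplant DNA, a chimerism check or an exemption for stem cell recipients.

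**Step 2: can the affected patients be identified?**

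| Field | Identifies a stem cell recipient? | Separates allogeneic from autologous? |
|---|---|---|
| Table 1 transplant footnote | No (solid organs only) | No |
| Table 1 medical history | No (solid organ only) | No |
| Table 2 underlying condition; Section 12 underlying conditions | Yes, if entered there | Not specified |
| Annex 3 tick box | Yes, for vaccinated patients | No |

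Stem cell status can be found. Graft type cannot be found from any listed field.

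**Step 3: how large is the effect on a pooled common-variant estimate?** Let f be the share of sequenced patients with an allogeneic graft, and r the correlation between donor and recipient genotype. Both are assumptions. Take r = 0.5 for a sibling donor and r = 0 for an unrelated donor. A true per-allele effect is then multiplied by

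(1 − f) + f·r = 1 − f(1 − r).

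| f (assumed) | Sibling, r = 0.5 | Unrelated, r = 0 |
|---|---|---|
| 2% | 1 − 0.02 × 0.5 = 0.99 | 1 − 0.02 × 1 = 0.98 |
| 10% | 1 − 0.10 × 0.5 = 0.95 | 1 − 0.10 × 1 = 0.90 |
| 20% | 1 − 0.20 × 0.5 = 0.90 | 1 − 0.20 × 1 = 0.80 |

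For scale, Section 9 gives about 19,784 subjects in all. If all were sequenced, 2% would be 0.02 × 19,784 ≈ 396 allogeneic recipients and 20% would be ≈ 3,957. The cohort descriptions name stem cell recipients for one partner only, as one of several populations there, so the upper rows are not credible for the whole cohort. They could apply only to a small sequenced subset rich in such patients.

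**Step 4: rare variants.** Under the same assumptions, a rare inherited variant read from the blood of an allogeneic recipient is also the patient's own with probability about 0.5 for a sibling donor and close to 0 for an unrelated donor. Dilution across the cohort does not repair this, because each carrier counts individually.

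**The case against.** Several counter-arguments have force.

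- **Collection is not analysis.** Section 11 requires collection and storage at visits; it does not say that every patient is sequenced. Data capture is modular, with Level II items adapted to each cohort, and the level of the genetic row cannot be read in the available text. Annex 4 also requires specific consent for genetic work, and it describes the methylation task as infected patients plus a few controls. A reader might infer that donor genotypes enter in every cohort. The documents do not support that. The point concerns only allogeneic recipients who are in fact sequenced.
- **Stem cell recipients can be found.** A reader might infer that analysts could not tell whom to set aside. That goes too far. Annex 3 and the underlying-condition fields can identify all stem cell recipients, and source records can be queried. What remains is that, without graft type, the safe course would also discard autologous recipients, whose blood DNA is their own.
- **Donor genotype can be the relevant one.** Section 6 is concerned with the pathways that vaccination switches on or off. In an engrafted patient the responding immune cells carry the donor genome, so blood genotype and methylation are informative for effects acting through those cells. This stands, and it argues for a separate, labelled analysis rather than removal. It does not make the genotype the patient's inherited one.
- **The formula is rough.** Donors are usually chosen for HLA match, so the sharing values above do not hold in that region.
- **Handling a stratum is analysis-plan content.** This is partly right. Section 13 describes no genetic association analysis, so the protocol never says that these genotypes will be pooled as host germline. The missing data field, however, is a protocol matter.

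A reader might also extend the point to blood cancers, where acquired variants in blood can resemble inherited ones. The protocol contains nothing wrong on that; filtering such calls is routine and belongs in an analysis plan.

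**Conclusion.** The point holds in a limited form. Stem cell transplant recipients are enrolled, blood is the only listed source of host DNA, no exemption or alternative source appears, and no listed field records whether a graft was allogeneic or autologous. In any allogeneic recipient who is sequenced, the blood genotype cannot be taken as the patient's inherited genotype.

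The number affected cannot be derived. It ranges from none, if all grafts are autologous, to every stem cell recipient sequenced. The effect on pooled common-variant estimates is probably small: 0.98 to 0.99 of the true effect at an assumed 2% share. The material risks are rare variants attributed to the wrong person and passed to functional work, and an inherited-versus-acquired contrast that fails for these patients.

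The conclusion assumes that some enrolled recipients have allogeneic grafts, which the documents neither state nor rule out. It also assumes that the case report form follows the listed fields; the form itself is not shown.

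**What to change.** 1. In the Table 1 footnote on transplant information, add the option *haematopoietic stem cell (allogeneic/autologous), date*, and carry it into the case report form.
2. In Section 11 and Table 3, state that blood DNA from allogeneic stem cell recipients is not used as host germline genotype unless stored pre-transplant DNA exists. State also that their blood genotype and methylation are analysed separately and labelled as donor-haematopoietic.

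The cost is one data field and a short statement, with no extra sampling. A few sequenced patients leave the host-germline analysis. Autologous recipients can stay in it, which would not be possible if all stem cell recipients had to be dropped for want of graft type.

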12. STUDY VARIABLES

Endpoint variables:

- Infection with SARS-CoV2 detected by RT-PCR on respiratory/saliva specimens;
- Reinfection and/or clinical relapse defined according to recent proposed definitions (7);
- Clinical spectrum of COVID-19 according to WHO mild, moderate, severe, and critical criteria (<https://www.who.int/publications/i/item/WHO-2019-nCoV-clinical-2021-1>);
- Duration of viable viral shedding in fragile patients diagnosed with COVID-19;
- Immune response in patients diagnosed with and/or vaccinated against COVID-19 assessed according to study protocol procedures (see above);
- All-cause mortality during the follow-up period;
- Change in basal clinical condition assessed by questionnaire on functional status and/or according to specific parameters of underlying fragile condition (i.e. graft function, cancer stage etc).

Baseline variables will include:

- Demographic data (sex, date of birth, ethnicity, blood group);
- Underlying conditions;
- Vaccination status against respiratory infectious diseases (i.e. Influenza, pneumococcus, BCG) if available.

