13. STATISTICAL ANALYSIS

We will carry out comprehensive descriptive analyses taking into account sociodemographic factors and clinical courses. The frequency distributions of the characteristics will be given in absolute and relative numbers, median plus interquartile range (IQR) or mean values plus 95% confidence interval (CIs). Associations with specific epidemiological features, laboratory results, therapeutic and preventive (including vaccination) strategies will be analysed using chi-square tests, t-tests or Mann-Whitney tests, depending on the data. To evaluate potential risk factors, multivariate regression models will be carried out. Outcome time analyses using Cox proportional-hazards regression models with time-dependent covariates will be performed to examine factors associated with each endpoint (including death). In addition, we will use cumulative incidence functions, such as the Fine-Gray sub-distribution hazard regression model, to account for competing events (i.e., death in evaluating graft function etc.). For missing values, a different strategy to understand the causes and the significance for the analysis will be developed and a graduated procedure for dealing with censorship and imputations via linked regressions will be developed. The significance level is defined with a p-value <0.05. Risk perception and socio-economic factors will be analysed using quasi-

experimental techniques (eg: propensity score matching, difference-in-differences) by exploiting several sources of variation over time and across individuals. All statistical analyses will be carried out with STATA, Python and/or R statistics software by trained staff (epidemiologists, statisticians) using the latest analysis methods.

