|--------------------------------|---|
| Project Acronym: | ORCHESTRA |
| Project Title: | Connecting European Cohorts to Increase Common and Effective Response to SARS- CoV-2 Pandemic |
| Coordinator: | UNIVR |
| Grant Agreement Number: | 101016167 |
| Funding Scheme: | Horizon 2020 |
| Start: | 1st December 2020 |
| Duration: | 36 months |
| Website: | www.orchestra-cohort.eu |
| Email: | [contact] |

Document Classification

| | |
|--------------------------------------|---|
| WP No: | WP6 |
| Deliverable No: | D6.1 |
| Title: | Standardised protocol and manual on collection and storage of samples |
| Lead Beneficiary: | UANTWERPEN |
| Other Involved Beneficiaries: | UNIBO, INSERM, HMGU |
| Nature: | Report, |
| Dissemination Level: | Confidential |
| Due Delivery Date: | M6 / 31 May, 2021 |
| Submission Date: | 31 May, 2021 |
| Justification of delay: | N/A |
| Status: | Final |
| Version: | 1.0 |
| Author(s): | [name], [name] |

History of Changes

| Version | Date | Created/Modified by |
|---------|------|--|
| 1 | | [name], [name] |

Table of contents

| | |
|-------------------------------|---|
| Executive summary | 3 |
| WP Context..... | 3 |
| Purpose of the document | 3 |
| Content of the document | 3 |
| Target of the document | 4 |
| Dissemination level..... | 4 |
| Core content..... | 4 |
| References | 4 |
| Acknowledgments | 4 |
| Appendix 1..... | 5 |

Executive summary

WP Context

The objective of WP6 in the ORCHESTRA project is to study human (epi)genetic, immunological, microbial, and viral features to identify markers of disease severity and to study the long-term impact of SARS-CoV-2 infection as well as the effect of immunization and characteristics underlying breakthrough infections post vaccination. Samples will be included retrospectively as well as prospectively within the study to study severe COVID-19 infection in hospitalized and outpatients during the acute disease stage as well as study long-term effects of infection and immunization on the host immune response.

Purpose of the document

The purpose of the WP6 protocols is to provide an overview of the biosamples to be collected within the prospective ORCHESTRA study, at which timepoints, and which analyses these samples are to be subjected to.

Content of the document

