2.1 CHARACTERISATION OF SARS-COV-2 VIRAL VARIANTS (TASK 6.2)

This task will target two main points among selected patient populations: [i] to characterise the viral variants and to identify variants of concern (VOCs) by whole genome sequencing (WGS) in COVID-19 patients and in vaccinated individuals with breakthrough infections, and [ii] to study potential

mutation selection in populations presenting with long viral replication or receiving immunoglobulin therapies, and [iii] to study the viral replication (viral load and excretion duration).

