3. SAMPLE TIMEPOINTS

An overview of sample types to be collected at each time point can be found in Table 1 below. No collection material will be provided within this study, but recommended materials to be used for each collection can be found in the section entitled “Detailed sample collection and storage instructions”.

Table 1. Overview of required biosamples associated analysis within WP6. Task numbers correspond to tasks described in the Description of Work, Amendment 1, Annex 1.

| Sample type | Task | Analysis |
|--------------------------------------|----------|---|
| NP swab | Task 6.2 | Viral variant sequencing |
| | Task 6.9 | Respiratory microbiome analysis |
| Serum | Task 6.3 | Serology |
| | Task 6.6 | Assessment of auto-antibodies against type I IFNs |
| EDTA plasma | Task 6.5 | Cytokine analysis |
| Heparin blood (PBMCs) | Task 6.4 | Cellular immunity characterization |
| EDTA whole blood | Task 6.6 | Human WGS or WES |
| | Task 6.7 | Epigenomics |
| Stool sample (faeces or rectal swab) | Task 6.8 | Intestinal microbiome analysis |

3.1 SAMPLING TIMEPOINTS FOR COVID-19 PATIENTS (INCLUDING REINFECTIONS AND BREAKTHROUGH INFECTIONS IN VACCINATED INDIVIDUALS)

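### Section 12 makes the duration of viable viral shedding an endpoint, but the protocol and Annex 4 as shown name no test of viability, only detection, load and sequencing of virus

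*Protocol*

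**What the plan says.** Section 12 of the protocol gives seven endpoint variables. The fourth is "Duration of viable viral shedding in fragile patients diagnosed with COVID-19". No assay, sampling rule or rule for the end of shedding accompanies it. Several neighbours are better anchored: infection is tied to RT-PCR, reinfection to a cited set of definitions, severity to WHO criteria, and immune response to the study procedures.

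Section 13 says that Cox regression with time-dependent covariates "will be performed to examine factors associated with each endpoint (including death").

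Section 11 describes what happens to respiratory samples. At visits for the underlying condition there is "Screening for past and/or current COVID-19 disease by medical interview, serology determination and nasopharyngeal swab or saliva" sampling, together with storage of "nasopharyngeal samples for SARS-CoV-2 detection and variant identification if clinically relevant". For post-vaccination monitoring and breakthrough infection it adds: "Nasal swabs for characterization of viral markers and respiratory microbiome dynamics will be sent to University of Antwerpen or INSERM".

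Annex 4 says, under its purpose, that it gives the samples to be collected, "at which timepoints, and which analyses these samples are to be subjected to". Its closest text to the endpoint is the third aim of Task 6.2 (Annex 4, Section 2.1): "to study the viral replication (viral load and excretion duration").

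**The concern.** Duration of viable shedding states how long a patient sheds virus that can infect others. To report it, a study needs either a test of infectivity on serial samples or a declared substitute for one. If the study holds only positive and negative molecular results, the quantity it can estimate is how long viral RNA stays detectable, which is a different quantity.

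The distinction matters in this population. The cohorts include transplant recipients, patients with cancer and patients with HIV, for whom a statement about the length of infectious shedding could be read as evidence about transmission. If RNA detection were reported under the Section 12 label, the label would claim more than the tests show. A statistical analysis plan can define censoring, intervals and models, but it cannot turn a detection result into a measurement of infectivity.

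**Working it through.** No arithmetic applies. The check sets every description of virus measurement beside the endpoint and asks whether it bears on viability.

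| Place | What is done with the virus or swab | Measures viability? |
|---|---|---|
| Protocol 3.2, Table 1 | Molecular test at baseline, conditional at later visits; sequencing of swabs | No |
| Protocol 3.2, Table 2 | Sequencing of swabs around vaccination | No |
| Protocol 11, visits for the underlying condition | Screening swab or saliva; detection and variant identification | No |
| Protocol 11, infection after vaccination | Detection in a respiratory or saliva sample | No |
| Protocol 11, samples sent out, and Table 3 | Viral markers and respiratory microbiome | No |
| Protocol 12, infection endpoint | RT-PCR | No |
| Annex 4, Task 6.2 | Whole genome sequencing, mutation selection, viral load, length of excretion | No |
| Annex 4, Task 6.9 | Sequencing of the respiratory microbiome; long-term carriage | No |
| Annex 4, Section 3, Tables 1 to 3 | Sequencing and microbiome analysis of the swab | No |

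Three items might look like a viability test:

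1. Annex 4, Section 2.3 (Task 6.4) mentions viability. It does so in a flow-cytometry panel for T and B cells, so it does not refer to virus.
2. Annex 4, Section 2.2 (Task 6.3) and protocol Section 11 plan neutralisation assays on serum. These characterise the patient's antibody response, not the virus the patient sheds.
3. Annex 4, Section 4.1.1 accepts a viral transport medium for swabs. No culture step is attached to it, and protocol Table 3 lists other storage solutions.

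Nor does any section give a cycle-threshold, viral-load or subgenomic-RNA rule as a proxy for viability.

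Task 6.2 is therefore the nearest planned measurement. It concerns selected patient populations, and its wording lacks *viable*. Section 12 applies the stronger term to fragile patients with COVID-19 in general.

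Two details govern any restatement. First, Day 0 in protocol Table 1 (footnote 1) is the first positive test of any kind. Annex 4, Table 2 limits it to PCR, and the EPICO cohort (Section 9.8.3) accepts confirmation by PCR or serology. A duration of RNA detection therefore has to start at a positive molecular test. Second, a swab used only for sequencing is not an RT-PCR result and should not be counted as one.

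**The case against.** The strongest reply is that the study does plan relevant data. Task 6.2 commits to viral load and to the length of excretion, Task 6.9 looks at long-term carriage, and an analysis plan or laboratory plan that is not shown could set a viral-load rule as a proxy. Section 11 also allows viral analyses in local laboratories. This stands in part. A reader might infer that the endpoint will have no data at all, and the documents do not support that: detection and load data are planned, load in selected populations. But a load rule would still be a proxy that the protocol does not mention, and it would not justify the unqualified word *viable* for all fragile patients with COVID-19.

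A reader might also take the silence of Annex 4, Table 1 as proof that no viability test is done. That table is headed "Overview of required biosamples associated analysis within WP6" and is not exhaustive: it lists neither RT-PCR nor viral load, although both are planned elsewhere. The point rests on the whole text shown, not on that table.

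A third tempting reading is that Table 1 stops testing before clearance. Its asterisk footnote repeats a test when the previous result was abnormal or when clinically indicated. On the natural reading, a positive patient is tested again at the next visit. Timing is coarse, but testing does continue while the patient is positive.

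Finally, the Cox sentence in Section 13 is generic and also covers endpoints, such as immune response, that are not naturally times to an event. That is fair. It shows that inference on this endpoint is within the plan, not that a specific shedding model was designed.

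**Conclusion.** The concern holds in this form: Section 12 names an endpoint about infectious virus, while the protocol and Annex 4 as shown provide only detection, load and sequencing, with no infectivity assay and no stated proxy. Reported from these tests, the endpoint would present RNA detection as infectious shedding.

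The scope is minor. It is one of seven endpoint variables, and none of the objectives in the synopsis or Section 7 depends on it. Still, the wording determines what the study may conclude, and correcting it is cheap, so the change should be made.

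The conclusion assumes that no viability assay is described in the Section 15 substudies, which appear by title only. Even if one were, Section 12 does not confine the endpoint to a substudy.

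**What to change.** In Section 12, delete *viable* and restate the endpoint as duration of SARS-CoV-2 RNA detection, which brings it into line with Task 6.2. Specify that:

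- time starts at the first positive molecular test, and patients confirmed by serology alone are excluded from this endpoint;
- the end of detection is taken from molecular tests already performed: the Table 1 molecular-test row, screening swabs and clinically indicated swabs;
- sequencing-only swabs do not count as RT-PCR results;
- the end of detection is known only to lie within an interval, with the analysis detail left to the statistical analysis plan.

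The alternative is to drop the endpoint. If infectivity is really intended, the protocol would have to name the assay, or a proxy with its threshold, and say which samples and patients it covers; an assay would be a new procedure.

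Dropping the endpoint or deleting the adjective is a wording change. The full restatement also needs molecular test dates wherever the eCRF does not already hold them, across 29 cohorts and partly retrospectively from February 2020. No new visit or assay is required. The price is that the result concerns RNA detection, not infectivity, and is imprecise in time, most of all for patients with few swabs.
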